### **6.6.2. Management of Participants with Gastrointestinal Symptoms**

Participants who experience intolerable GI symptoms (for example, nausea, vomiting, or diarrhea) at any time during the study, should first be counseled on dietary behaviors that may help mitigate nausea and vomiting (for example, eating smaller meals, splitting 3 daily meals into 4 or more smaller ones, and stopping eating when they feel full). If symptoms persist, the participant should be prescribed, at the investigator's discretion, symptomatic medication (for example, antiemetic or antidiarrheal medication). A temporary interruption of study drug for 1 dose is permitted, provided the participant has taken the last 3 weekly doses. Study treatment should be resumed immediately, either alone or in combination with symptomatic medication, which can also be utilized to manage symptoms. Management of study drug after interruptions >1 dose is discussed in Section 7.1.1.

During the 36-week open-label tirzepatide lead-in treatment period, if intolerable GI symptoms (for example, nausea, vomiting, or diarrhea) persist despite the above measures, the investigator should contact Lilly to consider a dose de-escalation step with subsequent re-escalation (Section 4.1.1.2.2). During the 52-week, post-randomization treatment period, dose de-escalation with subsequent re-escalation or dose de-escalation to a lower maintenance dose is not permitted. Those with intolerable GI symptoms that develop after randomization and persist despite the above measures (for example, dietary counseling, symptomatic medication, and interruption of study drug for 1 dose) should discontinue study drug but remain in the study for continued follow-up.

## **6.7. Intervention after the End of the Study**

Tirzepatide will not be made available to participants after conclusion of the study.

## 7. Discontinuation of Study Intervention and Participant Discontinuation/Withdrawal

### 7.1. Discontinuation of Study Intervention

In rare instances, it may be necessary for a participant to permanently discontinue (definitive discontinuation) study intervention. If study intervention is definitively discontinued during the open-label lead-in period, the participant will not be randomized and will be permanently discontinued from study. If study intervention is definitively discontinued after randomization, the participant will remain in the study to be evaluated for any trial endpoint at the end of the study. See the SoA for data to be collected at the time of discontinuation of study intervention and follow-up and for any further evaluations that need to be completed.

Possible reasons leading to permanent discontinuation of study intervention:

- **Participant decision**
  - The participant requests to discontinue study intervention
- **Clinical considerations**
  - Initiation of open-label GLP-1R agonist or DPP-4 inhibitor, if participant will not or cannot discontinue them
  - Intolerable GI symptoms despite management as described in Section 6.6.2
  - BMI  $\leq 18.5$  kg/m^2 is reached at any time during the treatment period

**Note:** The investigator should contact the sponsor CRP to discuss whether it is medically appropriate for the participant to continue study treatment.

- Diagnosis of T1DM
- Diagnosis of MTC or MEN syndrome type 2
- Significant elevation of calcitonin (Section 8.3.2.4)
- Diagnosis of acute or chronic pancreatitis
- Diagnosis of an active or untreated malignancy (other than basal or squamous cell skin cancer, in situ carcinomas of the cervix, or in situ prostate cancer)
- If the investigator, after consultation with the sponsor-designated medical monitor, determines that a systemic hypersensitivity reaction has occurred related to study drug administration, the participant should be permanently discontinued from the investigational drug
- Onset of pregnancy in a female participant
- Occurrence of any other treatment-emergent AE (TEAE), SAE, or clinically significant finding for which the investigator believes that permanent study drug discontinuation is the appropriate measure to be taken
- Inadvertent enrollment if continued treatment with study drug would not be medically appropriate
- PHQ-9 score  $\geq 15$ 
  - Participants should be referred to a mental health professional (MHP) to assist in deciding whether the participant should be discontinued from study drug. If

a participant's psychiatric disorder can be adequately treated with psycho- and/or pharmacotherapy, then the participant, at the discretion of the investigator (in agreement with the MHP), may be continued in the trial on randomized therapy.

- In addition, study drug may be discontinued if participants:
  - answered "yes" to Question 4 (Active Suicidal Ideation with Some Intent to Act, Without Specific Plan) on the "Suicidal Ideation" portion of the C-SSRS
    - or**
  - answered "yes" to Question 5 (Active Suicidal Ideation with Specific Plan and Intent) on the "Suicidal Ideation" portion of the C-SSRS
    - or**
  - answered "yes" to any of the suicide-related behaviors (actual attempt, interrupted attempt, aborted attempt, preparatory act or behavior) on the "Suicidal Behavior" portion of the C-SSRS

**Note:** A psychiatrist or appropriately trained professional may assist in the decision to discontinue the participant.

- **Discontinuation due to a hepatic event or liver test abnormality**
  - Participants who are discontinued from study intervention due to a hepatic event or liver test abnormality should have additional hepatic safety data collected via eCRF
  - Discontinuation of the study intervention for abnormal liver tests **should be** considered by the investigator when a participant meets one of the following conditions after consultation with the Lilly-designated medical monitor:
    - ALT or aspartate aminotransferase (AST)  $>8X$  ULN
    - ALT  $>2X$  baseline value **or**  $\geq 300$  U/L, whichever occurs first, if baseline ALT  $\geq 2X$  ULN
    - ALT or AST  $>5X$  ULN for more than 2 weeks
    - ALT or AST  $>3X$  ULN and TBL  $>2X$  ULN or international normalized ratio (INR)  $>1.5$
    - ALT or AST  $>3X$  ULN with the appearance of fatigue, nausea, vomiting, right upper-quadrant pain or tenderness, fever, rash, and/or eosinophilia ( $>5\%$ )
    - ALP  $>3X$  ULN
    - ALP  $>2.5X$  ULN and TBL  $>2X$  ULN
    - ALP  $>2.5X$  ULN with the appearance of fatigue, nausea, vomiting, right upper-quadrant pain or tenderness, fever, rash, and/or eosinophilia ( $>5\%$ )

Participants who stop the study drug permanently postrandomization and prior to 88 weeks should continue to attend all scheduled study visits to collect all planned efficacy and safety

measurements. Participants who stop the study treatment postrandomization and prior to 88 weeks, but are unwilling to attend remaining scheduled visits, should return for Visit 99 for a final weight measurement. If these participants are unwilling to attend Visit 99, their refusal to attend should be documented in the patient medical record.

See the SoA for data to be collected at the time of intervention discontinuation and follow-up and for any further evaluations that need to be completed.

### 7.1.1. Temporary Discontinuation

In certain situations, the investigator may need to temporarily interrupt study drug. Every effort should be made by the investigator to maintain participants on study drug and to restart study drug after any temporary interruption, as soon as it is safe to do so. Distribution of study medication at the correct dose will be per IWRs instructions.

If study drug interruption is....	and...	then participant...
2 consecutive doses or less	occurs between Weeks 0 and 36	restarts study drug at last administered dose, as per escalation schedule.
2 consecutive doses or less	occurs between Weeks 36 and 88	restarts study drug at chosen MTD at randomization.
3 consecutive doses or more	occurs between Weeks 0 and 36	is not randomized and will be discontinued from study.
3 consecutive doses or more	occurs between Weeks 36 and 88	restarts study drug at 5 mg and repeats dose-escalation scheme to achieve the same MTD assigned at randomization.

Abbreviation: MTD = maximum tolerated dose.

If study drug interruption is due to an AE, then the event is to be documented and followed according to the procedures in Section 10.4 of this protocol.

If study drug interruption is due to intolerable persistent GI AE, participants should be treated as suggested in Section 6.6.2.

Investigators should inform Lilly that study drug has been temporarily interrupted. The data related to temporary interruption of study treatment will be documented in source documents and entered on the eCRF.

### 7.2. Participant Discontinuation/Withdrawal from the Study

To minimize the amount of missing data and to enable assessment of study objectives as planned in the study protocol, every attempt will be made to keep randomized participants in the study irrespective of the following:

- adherence to or discontinuation from study drug

- adherence to visit schedule
- missing assessments
- study drug discontinuation due to AE
- development of comorbidities
- development of clinical outcomes

The circumstances listed above are **not** valid reasons for discontinuation from the study.

A participant may withdraw from the study:

- at any time at his/her own request
- at the request of his/her designee (for example, parents or legal guardian)
- at the discretion of the investigator for safety, behavioral, compliance, or administrative reasons
- if enrolled in any other clinical study involving an IP or enrolled in any other type of medical research judged not to be scientifically or medically compatible with this study
- if the participant, for any reason, requires treatment (for example, pharmacological, device-based, or surgical) that has been demonstrated to be effective for treatment of the study indication, discontinuation from the study occurs prior to introduction of the new treatment.

A participant will withdraw from the study:

[figure not shown]
- if a female participant becomes pregnant
- if study intervention is definitively discontinued during the open-label lead-in period, the participant will not be randomized and will be permanently discontinued from study.

Participation in the study can be stopped for medical, safety, regulatory, or other reasons consistent with applicable laws, regulations, and Good Clinical Practice (GCP). Participants who agree to provide information relevant to any trial endpoint at the end of the study are not considered to have discontinued from the study.

At the time of discontinuing from the study, if possible, an ED visit should be conducted, as shown in the SoA. See SoA for data to be collected at the time of study discontinuation and follow-up and for any further evaluations that need to be completed. The participant will be permanently discontinued both from the study intervention and from the study at that time.

If the participant withdraws consent for disclosure of future information, the sponsor may retain and continue to use any data collected before such a withdrawal of consent. If a participant withdraws from the study, he/she may request destruction of any samples taken and not tested, and the investigator must document this in the site study records.

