#### Rationale:

Obesity is a chronic disease and its increasing prevalence is a public health concern associated with rising incidence of Type 2 diabetes mellitus (T2DM), increased risk for premature death, and increased risk for some cancers (American Medical Association [AMA] 2013; Council on Science and Public Health 2013; Lauby-Secretan et al. 2016). Although loss of 5% to 10% body weight through lifestyle approaches, based on caloric restriction, physical activity, and behavioral therapy, has been shown to reduce obesity-related cardiovascular risk factors, and in some cases improve health-related quality of life (Mertens and Van Gaal 2000; Knowler et al. 2002; Jensen et al. 2014; Kolotkin and Andersen 2017), lifestyle therapies alone fail to achieve sustainable weight loss in the majority of patients with obesity (Dombrowski et al. 2014). Caloric restriction, for example, has been shown to lead to metabolic adaptive responses, including increases in hunger hormones, decreases in satiety factors (including gastrointestinal [GI] peptides), increased appetitive drive and food intake, and lower energy expenditure (Leibel et al. 1995; Sumithran et al. 2011). These adaptations are thought to work in concert to cause regain and poor durability of treatment.

The gut incretin hormones, glucose-dependent insulinotropic polypeptide (GIP) and glucagon-like peptide-1 (GLP-1), are secreted after meal ingestion and mediate the incretin effect. Both hormones have effects on endocrine cells in the pancreas, increasing insulin biosynthesis and secretion, and modifying glucagon secretion (Skow et al. 2016). Based on these properties, several GLP-1 receptor (GLP-1R) agonists have been approved for pharmacological treatment of T2DM (Tomlinson et al. 2016).

In addition to its pancreatic effects, GLP-1R activation decreases gut motility, slows gastric emptying, and promotes satiety (presumably through a combination of GLP-1R activation in the central and peripheral nervous systems), thereby regulating food intake and body weight (Baggio and Drucker 2007). The US Food and Drug Administration and the European Medicines Agency approved the GLP-1R agonist liraglutide for the treatment of overweight and obesity (SAXENDA® package insert, 2014; SAXENDA summary of product characteristics, 2015).

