**Note:**

- Visit 2 baseline assessments must be completed before processing in the interactive web-response system (IWRS).
- The visit date is determined in relation to the date of Visit 2 ( $\pm$  the visit interval tolerance).
- Visit 99 is only applicable to participants who discontinue the double-blind study treatment prematurely (after Week 36 and before Week 88) and decline to complete the remaining scheduled study visits. Participants wanting to discontinue the study treatment after randomization and before Week 88 will be asked to return for Visit 99 (88 weeks  $\pm$  7 days after Visit 2) primarily for body weight measurement and assessment of adverse events. If the participant is unwilling to attend Visit 99, it should be documented in the participant medical record that the participant has refused to attend.
- Participants who are unable or unwilling to continue the study treatment for any reason will perform an ED visit. If the participant is discontinuing during an unscheduled visit or a scheduled visit, that visit should be performed as an ED visit.
- For all office visits, remind participants to report to the site in a fasting condition, after a period of approximately 8 hours without eating, drinking (except water), or any significant physical activity. Since some screening procedures need to be completed in the fasting state, Visit 1 may be conducted over more than 1 day to ensure necessary conditions are met.
- Visit 801 (safety follow-up visit) should be performed 4 weeks after the last visit of the participant's treatment period.

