**Examples include, but are not limited to:**

- Saxenda (liraglutide 3.0 mg)
- Xenical®/Alli® (orlistat)
- Meridia® (sibutramine)
- Acutrim® (phenylpropanolamine)
- Sanorex® (mazindol)
- Apidex® (phentermine)
- BELVIQ® (lorcaserin)
- Bontril® (phendimetrazine)
- Qsymia™ (phentermine/topiramate combination), or
- Contrave® (naltrexone/bupropion)

*Note:* Use of metformin or any other glucose-lowering medication, whether prescribed for polycystic ovary syndrome (PCOS) or diabetes prevention, is not permitted.

35. Have started implantable or injectable contraceptives (such as Depo Provera®) within 18 months prior to screening

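### Protocol 7.1 and a clause in 7.2 are not reconciled for a randomised participant who starts an obesity-effective GLP-1R agonist, so the Week 88 weight can be observed or missing depending on which passage a site follows

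*Protocol*

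**What the plan says.** Protocol 7.1 deals with stopping study drug. Among the possible reasons for permanent discontinuation it lists "Initiation of open-label GLP-1R agonist or DPP-4 inhibitor, if participant will not or cannot discontinue them". On what follows it says: "If study intervention is definitively discontinued after randomization, the participant will remain in the study to be evaluated for any trial endpoint". It adds that "Participants who stop the study drug permanently postrandomization and prior to 88 weeks should continue to attend all scheduled study visits", and that those who stop drug "but are unwilling to attend remaining scheduled visits, should return for Visit 99 for a final weight measurement". The note under the Schedule of Activities (1.3) gives the same fallback: "Participants wanting to discontinue the study treatment after randomization and before Week 88 will be asked to return for Visit 99".

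Protocol 7.2 deals with leaving the study. In a list of circumstances in which a participant may withdraw, the last item says that if a participant for any reason needs treatment shown to be "effective for treatment of the study indication, discontinuation from the study occurs prior to introduction of the new treatment". The section later describes a participant who discontinues from the study as off study drug and off study at the same moment. It also says that stopping study drug is not a valid reason for leaving, and that people who agree to supply endpoint information at the end do not count as having left.

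The synopsis rationale records that the US and European regulators "approved the GLP-1R agonist liraglutide for the treatment of overweight and obesity", and exclusion criterion 34 lists that product among medications that promote weight loss.

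In the SAP, the treatment regimen estimand (1.2.1) compares the arms whatever the adherence and handles any event leading to drug discontinuation by treatment policy. Section 4.1 ends participation at withdrawal and drops data dated later. Section 4.3.2.3 imputes a missing Week 88 value from participants of the same arm who were measured after stopping drug (retrieved dropouts).

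**The concern.** Stopping the drug and leaving the study are different events, and a treatment-policy estimand depends on keeping them apart. Here one event, starting an obesity-effective GLP-1R agonist, can bring a participant under both sections. Section 7.1 points towards a measured Week 88 weight. The 7.2 clause, if followed to exit, points towards a missing one.

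The primary endpoint would then be measured or imputed according to site practice. The retrieved-dropout pool is affected as well, since participants kept under 7.1 join it and participants who exit under 7.2 do not.

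**Working it through.** **1. Do the rules overlap?** Section 7.1 names GLP-1R agonists and DPP-4 inhibitors. The 7.2 clause covers treatment shown to be effective for the study indication. The documents do not describe DPP-4 inhibitors that way, but they do describe one GLP-1R agonist as approved for obesity. The overlap is therefore limited to obesity-effective agents, and within that limit it exists.

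**2. What does 7.2 require?** Three parts of the section pull differently:
- The list stem is permissive, and a separate list of mandatory withdrawals follows whose readable items do not include this one.
- The clause itself is directive: study discontinuation comes before the new treatment.
- The saving sentence keeps in the study anyone who agrees to give endpoint information.

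No readable text says which part governs, or tells a site to ask for the Week 88 weight before applying the clause.

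**3. Where does the weight go?**
- Participant kept (7.1): a weight at the scheduled visit or Visit 99 enters the FAS and can serve as a donor value for imputation.
- Participant exits (7.2): the weight is not taken, or is dropped under SAP 4.1 if dated after withdrawal, and Week 88 is imputed under SAP 4.3.2.3.

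The efficacy estimand is not affected for people who stop drug, because the EAS excludes off-drug data (after last dose plus 7 days) on either path.

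**4. The plan's own sizing (Protocol 9.2, SAP 5).** Inputs: 300 per arm, 25% dropout, difference 6, SD 8, two-sided alpha 0.05, t-test.
- Evaluable per arm = 300 × (1 − 0.25) = 225
- SE = 8 × √(2/225) = 0.754
- Noncentrality = 6/0.754 = 7.96, power above 99.9%

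The stated power of more than 90% is reproduced as a lower bound.

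**5. Illustration of size; p and R are assumed.** Let p be the net placebo excess leaving for other obesity treatment (1–10% of the arm, assumed). Let E be the effect of that treatment (3–7 points, the placebo-adjusted average for approved drugs in Protocol 2.2, perhaps too high for a start partway through 52 weeks). Let R be how much more the leavers had regained than the retrieved placebo dropouts (assumed). With donor mean m, and E and R taken as equal in both arms:

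Imputed − true = m − (m + R − E) = E − R, so the shift in the treatment difference is p × (E − R).

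- R = 0: from 0.01 × 3 = +0.03 to 0.10 × 7 = +0.70 points, or 0.5% to 11.7% of the planned 6
- R = 5, p = 10%: 0.10 × (−2 to +2) = −0.20 to +0.20
- R = 10: from 0.01 × (7 − 10) = −0.03 to 0.10 × (3 − 10) = −0.70
- Break-even at R = E: 3/8 = 0.38 to 7/8 = 0.88 of the planned SD

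A positive shift overstates the difference; a negative one understates it. If some donors are themselves on other obesity treatment, the R = 0 shift is smaller.

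**6. Does power suffer?**
- True difference 6 − 0.70 = 5.3: 5.3/0.754 = 7.03, power above 99.9%.
- Harsher assumption, 15% of placebo with a 12-point gap between true and imputed values: 0.15 × 12 = 1.8, leaving 4.2; noncentrality 5.57, power still above 99.9%.
- Losing a further 20% of the 300 placebo participants leaves 225 − 60 = 165 evaluable; at a difference of 6, power is again above 99.9%.

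**The case against.** A reader might infer that the two sections flatly contradict each other, with 7.1 keeping the participant and 7.2 removing them. The text does not support that. The 7.2 clause sits under a permissive stem, the section opens by committing to every effort at retention, and anyone who agrees to give endpoint data is not counted as having left. For such a participant both sections can lead to a measured Week 88 weight, and the SAP 4.1 cut-off need not apply.

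The overlap is also narrow. Section 6.5 names the same two drug classes as exceptions when a participant develops diabetes, so the 7.1 item probably concerns incident diabetes for the most part. The triggers differ in time too: 7.1 speaks of an agent already started, 7.2 of a need identified beforehand. The 7.2.1 disposition chart is the natural place to settle this and is not readable here; a figure is also missing within the mandatory-withdrawal list.

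On the numbers, nothing says that retrieved dropouts are free of other obesity treatment, and SAP 4.3.2.4 already plans a two-way tipping point analysis.

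All of this stands and narrows the point. It does not remove it. The saving sentence helps only those who agree to give data, and no readable passage tells a site to ask before applying the exit clause. The tipping point analysis tests the missing-data assumption but recovers no weights.

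**Conclusion.** The point holds in limited form. For a randomised participant starting an obesity-effective GLP-1R agonist, 7.1 and the 7.2 clause are not reconciled in the readable text, 7.2 is internally unclear, and the Week 88 weight can be observed or imputed as a result. Losing it fits poorly with an estimand defined regardless of adherence.

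The size is unknown. The documents give no rate of such starts, and the shift of −0.70 to +0.70 points rests on assumed inputs. A reader might infer that imputing these values favours tirzepatide by overstating placebo regain. That follows only if the leavers had regained little more than the donors and the donors are largely untreated; if those who leave were regaining most, the shift vanishes or reverses. Nor is superiority or power in doubt. The correction is worth making because it is cheap and protects the primary endpoint data. Confidence is medium, since the 7.2.1 chart could not be read.

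**What to change.** 1. Reconcile Protocol 7.1 with 7.2, together with the Schedule of Activities note and the 7.2.1 chart, so that stopping study drug or starting another treatment does not by itself end collection of the primary endpoint. This concerns weight collection only; all rules on starting, stopping or permitting treatment stay with the clinical team.
2. State that consenting randomised participants in this position are still asked for the Week 88 weight, at the scheduled visit or Visit 99.
3. State in SAP 4.1 that a weight obtained this way counts in the FAS and is not removed by the end-of-participation cut-off.
4. Add one line to SAP 1.2.1 on other obesity treatment started while study drug continues. This can arise because 7.1 stops drug only if the participant will not or cannot stop the agent. Events that lead to drug discontinuation are already covered there.

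The cost is a short protocol clarification with a site letter, two short SAP edits, and some extra Visit 99 weighings. Their number is unknown; if all leavers fall within the assumed dropout it is at most 0.25 × 600 = 150 across both arms, many of whom the protocol already asks to attend. If follow-up is complete when the change is made, only items 3 and 4 can still be applied.
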